## 1.4 Correlative Studies

### 1.4.1 Whole exome and transcriptome sequencing.

We will use whole exome and transcriptome deep sequencing (WES; RNAseq) in the pre-treatment, on treatment, and post-resistance samples to uncover somatic genetic alterations (mutations and copy number alterations) and transcriptional events associated with clinical resistance (either de novo or acquired), using our methods and with a minimum depth of WES coverage of 100X to capture events occurring down to ~1% frequency. This approach will enable identification and/or validation of RNA signatures of potential resistance events, such as ERK1/2 transcriptional output. The analysis of samples from patients with de novo resistance and of matched paired tumor samples acquired from individual patients before treatment and at acquired resistance (based on standard radiographic assessment in the trial, such as RECIST criteria) will be prioritized for study to facilitate the clinical correlation of the genetic findings with bona fide clinical resistance. Orthogonal validation of specific findings will be done using individualized assays in the clinical specimens (e.g. direct sequencing, SNP arrays, fluorescence in situ hybridization for DNA alterations; q-RT-PCR, IHC for RNA and protein abundance changes) and associated circulating free DNA, where feasible.

### 1.4.2 IHC for phospho-ERK and downstream effectors:

We will evaluate whether trametinib effectively shuts down the MEK signaling axis by performing IHC analysis on pre-treatment and on-treatment biopsy specimens. YAP-TAZ signaling will also be evaluated, given that its upregulation is associated with resistance to MAPK pathway inhibitors.

### 1.4.3 Patient-derived xenografts and organoids

When possible, patient derived xenografts or organoids will be generated from patient biopsy specimens. Alterations discovered in the clinical specimen analysis will be functionally studied using our standard cell-based assays. We will test if activation or suppression of the candidate resistance gene (as indicated by whether the gene is increased or decreased in resistance)

promotes MEK inhibitor resistance, in vitro and in vivo in tumor xenograft and organoid studies.

*Version date: 02-15-2018*

*Protocol CC#: 166521*

---

### 1.4.2 Cell-Free DNA

Blood samples for circulating tumor DNA (ctDNA) will be collected pre-treatment and post-resistance tissue biopsy to identify mechanisms of resistance. Concordance of ctDNA with pre- and post- tissue biopsy will be assessed. 20ml of whole blood for ctDNA analysis will be collected at the time of pre-treatment biopsy, monthly until tumor progression, and at the time of post-resistance biopsy to monitor dynamic changes in the quantity of ctDNA for the specific *NF1* mutations. The rate of ctDNA clearance of the specific *NF1* mutations will be serially tracked and will be compared to radiologic change on CT scans. Acquired somatic mutations in, *NF1* or off-target genes qualitatively evaluated to identify second site mutations that may confer resistance to therapy.

## 2 Objectives of the Study

### 2.1 Primary

To evaluate the efficacy of trametinib in patients with advanced, non-squamous NSCLC who have progressed on at least one prior systemic anti-cancer therapy (i.e. platinum doublet chemotherapy, anti-PD1 or anti-PDL1 immunotherapy, or appropriate EGFR, ALK, and ROS-1 targeted therapy) and whose tumors harbor a non- synonymous mutation in *NF1* and is negative for activating mutations in *KRAS*.

### 2.2 Secondary

- To evaluate secondary measures of clinical efficacy in advanced NSCLC patients treated with trametinib.
- To evaluate the safety and tolerability of trametinib using National Cancer Institute Common Toxicity Criteria (NCI-CTC) version 4.03.

### 2.3 Exploratory Objectives, Other Assessments

- Determine whether specific mutations in *NF1* identified in pretreatment tumor samples correlate with response and/or resistance to trametinib.
- To identify biomarkers of clinical benefit and mechanisms of resistance (de novo resistance, incomplete response, and acquired resistance) to trametinib therapy in *NF1* mutant NSCLC.
- Assess circulating tumor DNA (ctDNA) for biomarkers of response and/or resistance to trametinib.

## 2.4 Endpoints

### 2.4.1 Primary Endpoints

- Objective Response Rate (ORR) according to RECIST Version 1.1 criteria as determined by investigator assessment. The ORR is defined as the best overall response recorded from the start of the treatment until disease progression or recurrence from the start of treatment.

### 2.4.2 Secondary Endpoints

- Efficacy: DR, DCR, PFS, and OS according to RECIST Version 1.1 criteria as determined by investigator assessment.
  - The DR for CR and PR will be measured from the date that the best response is first recorded until the date that PD is documented. For patients who continue treatment post progression, the date of PD documentation will be used for analysis.
  - DCR will be defined as the percentage of patients who have achieved CR, PR, or SD for at least 12 weeks.
  - PFS will be calculated as 1+ the number of days from the first dose of study drugs to documented radiographic progression or death due to any cause over a period of 1 year. For patients who continue treatment post-progression, the date of radiographic progression will be used for PFS analysis.
  - OS will be calculated as 1+ the number of days from the first dose of study drugs to death due to any cause over a period of 1 year.
- Safety and tolerability:
  - All treatment-emergent AEs
  - Treatment-emergent AEs by CTCAE grade
  - Grade 3 or greater treatment-emergent AEs
  - Treatment-related, treatment-emergent AEs
  - Dose-limiting toxicity AEs
  - Serious treatment-emergent AEs
  - Treatment-emergent AEs with an outcome of death
  - Treatment-emergent AEs leading to discontinuation of trametinib.
  - Treatment-emergent AEs resulting in interruption or reduction or delay of trametinib.

### 2.4.3 Exploratory Endpoints

- Specific mutations in *NF1* identified in pretreatment tumor samples correlated with response and/or resistance to trametinib.
- Circulating cell free DNA (cfDNA) biomarkers associated with response and/or resistance to trametinib.
- RNA and DNA changes in samples during therapy and at progression.

## 3 Study Design

### 3.1 Characteristics

---

This is a Phase II, open-label, multicenter clinical trial evaluating the efficacy and safety of

[figure not shown]
trametinib monotherapy in patients with advanced non-squamous NSCLC whose tumors harbor  
Helen Diller Family Comprehensive Cancer Center

*Version date: 02-15-2018*

*Protocol CC#: 166521*

---

a non-synonymous *NF1* mutation and are wildtype for activating mutations in *KRAS*. Eligible patients must have documented disease progression either during or after treatment with appropriate EGFR, ALK, or ROS-1 inhibitors (in patients with EGFR activating mutations, or ALK or ROS-1 fusions) and platinum doublet chemotherapy (or inability to tolerate) or most recent therapy and must not have received prior treatment with a MEK inhibitor.

**Figure 3.1. Study schema**

Patients will receive trametinib monotherapy in 28-day cycles. The primary outcome is objective response rate.

### 3.2 Number of Subjects

A total of 27 patients will be enrolled in the study, with the goal of obtaining 24 evaluable patients. This will provide 80% power to detect a 30% ORR with trametinib compared to the null hypothesis of a 10% ORR. Using a Simon 2-stage design, if we do not observe at least 2 responses within the first 15 patients, enrollment will be stopped due to lack of efficacy.

### 3.3 Eligibility Criteria

Patients must have baseline evaluations performed prior to the first dose of study drug and must meet all inclusion and exclusion criteria. In addition, the patient must be thoroughly informed about all aspects of the study, including the study visit schedule and required evaluations and all regulatory requirements for informed consent. The written informed consent must be obtained

from the patient prior to enrollment. The following criteria apply to all patients enrolled onto the study unless otherwise specified.

### 3.3.1 Inclusion Criteria

1. Histologically or cytologically confirmed metastatic or unresectable locally advanced, non-squamous, NSCLC.
2. Documented non-synonymous somatic mutation in *NF1* in any tumor specimen or cell-free DNA assay by CLIA-approved laboratory.
3. Received at least one prior line of cancer therapy for the treatment of NSCLC. This should include at least one of the following: platinum (carboplatin or cisplatin) doublet chemotherapy (acceptable combinations include: paclitaxel, docetaxel, abraxane, pemetrexed, gemcitabine, vinorelbine, or etoposide), anti-PD1/PDL1 therapy (pembrolizumab, nivolumab, or atezolizumab), or appropriate targeted therapy in patients with activating EGFR (osimertinib, erlotinib, gefitinib, or afatinib), ALK (alectinib, crizotinib, ceritinib, brigatinib, or lorlatinib), or ROS-1 (crizotinib or entrectinib) alterations. Therapy may be given as monotherapy or in combination with other cancer therapy (e.g. bevacizumab, ipilimumab)
4. Patients with a known activating mutation in EGFR (Exon 19 deletion, G719A, S768I, V769L, T790M, L833F, L858R, L861Q), must have progressed or been intolerant to treatment with a first-line EGFR TKI (erlotinib, afatinib, gefitinib or osimertinib). Patients whose tumors were found to have an EGFR T790M mutation must also have progressed or been intolerable to treatment with osimertinib.
5. Patients with a known ALK-rearrangement must have progressed or been intolerant to treatment with at least one ALK TKI: crizotinib, ceritinib, alectinib, brigatinib, or lorlatinib.
6. Patients with a known ROS-1- rearrangement must have progressed or been intolerant to treatment with crizotinib or entrectinib.
7. Patients with PDL1 level of  $\geq 50\%$ , who do not have an ALK-rearrangement or EGFR-mutation, must have progressed or been intolerant to treatment with anti-PD1/PDL1 therapy (pembrolizumab, nivolumab, or atezolizumab).
8. Documented disease progression or intolerance to treatment either during or after treatment with most recent therapy.
9. Willingness to undergo research biopsy.
10. Measurable disease defined by RECIST 1.1 criteria.
11. Life expectancy of at least 3 months.
12. Eastern Cooperative Oncology Group (ECOG) performance status of 0 to 1.
13. Age  $\geq 18$  years.
14. Resolution of all acute toxic effects of prior chemotherapy, immunotherapy, radiotherapy or surgical procedures to NCI CTCAE Version 4.03 grade 1.
15. Adequate baseline organ function defined in Table 3.1.

**Table 3.1 Definitions for adequate baseline organ function**

| System                                | Laboratory Values           |
|--|------------------------------------|
| Hematologic                           |                                    |
| Absolute neutrophil count                    | □□ $1.2 \times 10^9/L$             |
| Hemoglobin                                   | □□ 9 g/dL                          |
| Platelets                                    | □□ $100 \times 10^9/L$             |
| PT/INR and PTT                               | ≤ 1.5 x ULN                        |
| Hepatic                               |                                    |
| Albumin                                      | □□ 2.5 g/dL                        |
| Total bilirubin                              | □□ 1.5 x ULN                       |
| AST and ALT                                  | □□ 2.5x ULN                        |
| Renal                                 |                                    |
| Creatinine or                         | □□ 1.5 ULN                         |
| Calculated creatinine clearance a | □□ 50 mL/min                       |
| Cardiac                               |                                    |
| Left Ventricular Ejection fraction (LVEF)    | ≥ LLN by ECHO or MUGA b |

ALT = alanine aminotransferase; AST = aspartate aminotransferase; INR = international normalized ratio; PT = prothrombin time; PTT= partial thromboplastin time; ULN = upper limit of normal; LLN = lower limit of normal

a. Calculated by the Cockcroft-Gault formula.

b. Same method as used at baseline must be use throughout the study

16. Women of childbearing potential must have a negative serum or urine pregnancy test within 3 days prior to study enrollment. The effects of trametinib on the developing human fetus are unknown. For this reason and because animal studies with trametinib have shown reproductive toxicity, women of child-bearing potential and men must agree to use effective methods of contraception (hormonal or barrier method of birth control) prior to study entry, for the duration of study participation, and for 4 months following discontinuation of trametinib. Should a woman become pregnant or suspect she is pregnant while she or her partner is participating in this study, she should inform her treating physician immediately. Men treated or enrolled on this protocol must also agree to use adequate contraception prior to the study, for the duration of study participation, and 4 months after completion of study drug administration.
17. Able to swallow and retain orally administered medication and does not have any clinically significant gastrointestinal abnormalities that may alter absorption such as malabsorption syndrome or major resection of the stomach or bowels.
18. All prior treatment- related toxicities must be CTCAE (Version 4.03) ≤ Grade 1 (except alopecia) at the time of randomization
19. Ability to understand a written informed consent document, and the willingness to sign it.

### 3.3.2 Exclusion Criteria

Patients eligible must not meet **any** of the following criteria:

1. Known mutation in KRAS at position G12, G13, or Q61.
2. Symptomatic or untreated leptomeningeal or brain metastases or spinal cord compression. Treated brain metastases are allowed as long as they are stable for at least 28 days post-treatment.
3. Pregnant women are excluded from this study because trametinib is a MEK inhibitor with the potential for teratogenic or abortifacient effects. Because there is an unknown but potential risk for adverse events in nursing infants secondary to treatment of the mother with trametinib, breastfeeding should be discontinued if the mother is treated with trametinib.
4. History of another malignancy.

**Exception:** Subjects who have been disease-free for 3 years, or subjects with a history of completely resected non-melanoma skin cancer and/or subjects with indolent second malignancies are eligible.

5. Any serious and/or unstable pre-existing medical disorder (aside from malignancy exception above), psychiatric disorder, or other conditions that could interfere with subject's safety, obtaining informed consent or compliance to the study procedures.
6. The subject has received cytotoxic chemotherapy, molecular targeted therapy, or immunotherapy within 21 days before the first dose of study drug (trametinib).
7. Prior treatment with MEK inhibitor.
8. History of interstitial lung disease or pneumonitis.
9. Have a known immediate or delayed hypersensitivity reaction or idiosyncrasy to drugs chemically related to study drug, or excipients or to dimethyl sulfoxide (DMSO).
10. Any major surgery, extensive radiotherapy, chemotherapy with delayed toxicity, biologic therapy, or immunotherapy within 21 days prior to study enrollment and/or daily or weekly chemotherapy without the potential for delayed toxicity within 14 days prior to study enrollment.
11. History of retinal vein occlusion (RVO).
12. Known Human Immunodeficiency Virus (HIV), Hepatitis B Virus (HBV), or Hepatitis C Virus (HCV) infection (subjects with laboratory evidence of cleared HBV and HCV infection will be permitted).
13. History or evidence of cardiovascular risk including any of the following:
  - LVEF < LLN
  - A QT interval corrected for heart rate using the Bazett's formula (QTcB)  $\geq$  480 msec;
  - History or evidence of current clinically significant uncontrolled arrhythmias.

- **Clarification:** Subjects with atrial fibrillation controlled (defined as not requiring change in cardiac drug dosing, emergency room visit, or hospital admission) for >30 days prior to dosing are eligible.
- History of acute coronary syndromes (including myocardial infarction and unstable angina), coronary angioplasty, or stenting within 6 months prior to study enrollment.
- History or evidence of current  $\geq$  Class II congestive heart failure as defined by New York Heart Association (NYHA).
- Treatment refractory hypertension defined as a blood pressure of systolic > 140 mmHg and/or diastolic > 90 mm Hg which cannot be controlled by anti-hypertensive therapy;
- Patients with intra-cardiac defibrillators.

### 3.4 Duration of Therapy

In the absence of treatment delays due to adverse events, treatment may continue for 24 months or until:

- Disease progression
- Inter-current illness that prevents further administration of treatment
- Unacceptable adverse event(s)
- Patient decides to withdraw from the study
- Significant patient non-compliance with protocol
- General or specific changes in the patients' condition render the patient unacceptable for further treatment in the judgment of the investigator.
- The study is closed by the sponsor or investigator.

Patients who are continuing to respond to the study drug after 24 months of therapy will be provided with continued access to the drug by Novartis.

### 3.5 Duration of Follow Up

Patients will be followed for 30 days after completion of treatment or removal from study, or until death, whichever occurs first. Patients removed from study for unacceptable treatment related adverse event(s) will be followed until resolution or stabilization of all treatment related adverse events to Grade 2 or lower.

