| 
Study Design
          | 
This is a phase II, single-arm, open-label, multicenter clinical trial evaluating the efficacy and safety of trametinib monotherapy in patients with advanced non-squamous NSCLC whose tumors non-synonymous NF1 mutations and are KRAS wildtype. Eligible patients must have documented disease progression either during or after treatment with platinum doublet chemotherapy or most recent therapy and may not have received prior treatment with a MEK inhibitor. Patients with activating alterations in EGFR, ALK, and ROS-1 must also have received appropriate TKI treatment. Patients who meet eligibility criteria will receive trametinib monotherapy and followed for the primary endpoint of objective response rate and additional secondary endpoints.
 
The diagram illustrates the study timeline. It is divided into four main phases: Screening, Enrollment, Treatment Period, and Endpoints. 
 Screening: Includes screening assessments for NF1-mutant, KRAS wt, Stage IV Non-squamous NSCLC, prior treatment and progression on at least one prior systemic cancer therapy, ECOG: 0-1, and a required research biopsy. 
 Enrollment: A vertical bar indicating the period of patient recruitment. 
 Treatment Period: Labeled 'Trametinib 2.0 mg PO daily (n = 27)'. It is divided into 'Cycle 1 (28d)' and 'Cycle 2 (28d) and future cycles'. Days 1, 15, and 28 are marked for Cycle 1. Days 1 and 28 are marked for Cycle 2. A research biopsy is performed at the first scan and end of treatment (optional), and imaging RECIST 1.1 assessment is performed every other cycle. 
 Endpoints: 
         - Primary: ORR (if < 2 responses within the first 15 patients, study will be closed). 
         - Secondary: Safety, Efficacy, DCR, 1-year PFS, 1-year OS, PK/PD. 
         - Correlative Studies: Compare pre- and on-treatment post-treatment biopsies: 1. Phospho-ERK (IHC), 2. Genomic alterations by exome seq, 3. Transcriptional programs by RNA seq, 4. PDx/organoid generation, 5. circulating tumor DNA assessment. 
 Safety Assessments: ECG, AEs, CBC, CMP are performed throughout the study.
 |

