| 
Number of patients
    | 
A total of 27 patients will be enrolled into the study, with the goals of obtaining 24 evaluable patients. Using a Simon 2-stage design, if we do not observe at least 2 responses within the first 15 patients, enrollment will be stopped due to lack of efficacy.
  |
| 
Duration of Therapy
   | 
Patients may continue treatment until disease progression or up to 24 months from the time of study entry or until the study is closed.
   |
| 
Duration of Follow up
 | 
All patients will be followed for 12 months.
  |
| 
Duration of study
     | 
The study is estimated to reach completion 4 years from the time the study opens to accrual.
  |

|                             |  |
|-----------------------------|--|
| 
Study Drugs
          | 
Trametinib is a reversible and highly selective allosteric inhibitor of MEK1 and MEK2 activation and kinase activity. Trametinib will be administered as 2 mg orally once daily.
  |
| 
Safety Assessments
   | 
Safety assessments will be based on events occurring during the on-study period, defined as from the first dose of trametinib to 30 days after the last dose of trametinib or until resolution for serious adverse events. Safety will be assessed by reviewing adverse events (AEs), laboratory evaluations, physical examination, and imaging or procedures when clinically indicated. Toxicity will be graded according to the National Cancer Institute's Common Terminology Criteria for Adverse Events (version 4.03).
  |

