| 
Efficacy Assessments
 | 
Efficacy measures will include tumor assessments by CT scans of the chest, abdomen, and pelvis with appropriate slice thickness per RECIST Version 1.1. Brain imaging (CT/MRI) is required at baseline and follow-up scans should include the brain in patients with baseline brain lesions. All sites of disease should be followed and the same imaging methodology should be used throughout the study. Tumor assessments will be carried out at screening and every 8 weeks <math>\pm</math> 1 week from the time of trametinib initiation and thereafter until tumor progression. Patients are required to have an end-of-treatment tumor scan using the same methodology used at screening unless:
 
 
• The patient has radiographic evidence of disease progression while on study, or
 
• It has been < 2 weeks since their last on-study scan
 
 
Patients who discontinue trametinib without progression should continue to be scanned per standard of care until disease progression occurs.
 |

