### 6.1.4 Post-treatment/Follow Up Visits

Patients will be followed every 3 months +/- 14 days for up to 18 months after enrollment or until disease progression.

The following procedures will be performed at the Follow Up Visit(s):

- Disease assessment including imaging (CT or MRI) of chest/abdomen/pelvis, and brain (if lesions found in screening) for tumor/lesion assessment. Scans would only be completed in follow-up for patients whose disease has not yet progressed since entering the study.
- Physical examination
- Vital signs
- Performance Status
- Evaluation of adverse events
- Concomitant medications
- Hematology labs (other than CBC w/ Diff)
- CBC with differential and platelet count
- Blood chemistry assessment, including:
  - Alkaline phosphatase, ALT/AST, total bilirubin, calcium, phosphorus, BUN, creatinine, total protein, albumin, fasting glucose, potassium, sodium, chloride, bicarbonate,
- Coagulation assessment, including PT/PTT/INR

- Urinalysis

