### **6.1.5 Long Term/Survival Follow-up Procedures**

### **6.1.6 Discontinuation of Therapy**

The Investigator will withdraw a patient whenever continued participation is no longer in the patient's best interests. Reasons for withdrawing a patient include, but are not limited to, disease progression, the occurrence of an adverse event or a concurrent illness, a patient's request to end participation, a patient's non-compliance or simply significant uncertainty on the part of the Investigator that continued participation is prudent. There may also be administrative reasons to terminate participation, such as concern about a patient's compliance with the prescribed treatment regimen.

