### 8.3.3

## Secondary Analysis (or Analysis of Secondary Endpoints)

### Definition and analytical plan for secondary efficacy endpoints:

**(a) Duration of response (DR):** The DR for CR and PR will be measured from the date that the best response is first recorded until the date that PD is documented over the period of 1 year. For patients who continue treatment post progression, the date of PD documentation will be used for analysis. The DR will be summarized using descriptive statistics (N, mean, standard deviation, minimum, and maximum).

**(b) Disease control rate (DCR):** DCR will be defined as the percentage of patients who have achieved CR, PR, or SD for at least 12 weeks. The DCR will be summarized using descriptive statistics (N, mean, standard deviation, minimum, and maximum).

**(c) Progression-free Survival (PFS):** PFS will be calculated as 1+ the number of days from the first dose of study drugs to documented radiographic progression or death due to any cause over a period of 1 year. For patients who continue treatment post-progression, the date of radiographic progression will be used for PFS analysis. The Kaplan-Meier analysis will be used to calculate the median PFS with 95% confidence interval.

**(d) Overall Survival (OS):** OS will be calculated as 1+ the number of days from the first dose of study drugs to death due to any cause over a period of 1 year. The Kaplan-Meier analysis will be used to calculate the median OS with 95% confidence interval.

**(3) Definition and analytical plan for safety and tolerability endpoints:** The safety population will consist of all subjects who receive any amount of study treatment. Safety will be assessed by evaluation of AEs. All safety analyses will be performed using the safety population. Adverse event terms recorded on the CRFs will be mapped to preferred terms using the Medical Dictionary for Regulatory Activities (MedDRA). Seriousness, severity grade and relationship to study treatment will be assessed by the investigator. Severity grade will be defined by the National Cancer Institute (NCI) CTCAE v4.03. Listings of AEs will be provided.

Separate tables will present the following by dose group and study phase:

- All treatment-emergent AEs
- Treatment-emergent AEs by CTCAE grade
- Grade 3 or greater treatment-emergent AEs
- Treatment-related, treatment-emergent AEs
- Dose-limiting toxicity AEs
- Serious treatment-emergent AEs
- Treatment-emergent AEs with an outcome of death

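### Section 3.5 ends follow-up 30 days after treatment without limiting that to safety, which conflicts with 12-month follow-up for all and leaves 1-year OS exposed

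*Combined protocol and SAP*

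**What the plan says.** The protocol gives three follow-up durations that do not agree.

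- **Section 3.5, the general follow-up rule:** "Patients will be followed for 30 days after completion of treatment or removal from study, or until death, whichever occurs first". The only extension is for resolving treatment-related adverse events. The sentence is not confined to safety.
- **Abstract, Duration of Follow up:** "All patients will be followed for 12 months". No starting point, interval or method is given.
- **Section 6.1.4:** "Patients will be followed every 3 months +/- 14 days for up to 18 months after enrollment or until disease progression". Table 6.1 also shows 3-monthly follow-up visits.

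The endpoints need about a year of data. The Abstract's study schema lists "Secondary: Safety, Efficacy, DCR, 1-year PFS, 1-year OS, PK/PD". Sections 2.4.2 and 8.3.3 measure OS "from the first dose of study drugs to death due to any cause over a period of 1 year", and PFS has the same window. Section 8.3.3 measures duration of response "until the date that PD is documented over the period of 1 year". It plans Kaplan-Meier estimates for PFS and OS and states no censoring rule.

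Section 6.1.5 consists of its title, "Long Term/Survival Follow-up Procedures", and is followed directly by Section 6.1.6. Nothing marks a redaction there. Table 6.1 has no row for survival status.

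For patients who stop early, the Abstract says: "Patients who discontinue trametinib without progression should continue to be scanned per standard of care until disease progression occurs". Section 6.1.4 and footnote f of Table 6.1 also keep scans going for patients who have not progressed.

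**The concern.** Most patients will stop trametinib at progression, well before most of the first-year deaths can be expected. A site that takes Section 3.5 at its word stops recording such a patient 30 days later. A site that follows the Abstract keeps recording to 12 months. Deaths would then be missed, and the two kinds of site would contribute different data to one OS curve.

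Kaplan-Meier assumes that censored patients have the same prognosis as those who remain. Censoring soon after a treatment stop breaks that assumption if the death hazard rises after stopping, and 1-year OS is then biased upward. Without any such rise the estimate is unbiased but much less precise.

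**Working it through.** **Step 1: which endpoint does each follow-up rule cover?**

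| Source | PFS and duration of response | OS after progression |
|---|---|---|
| Section 3.5 | cut 30 days after a stop without progression | cut 30 days after the stop |
| Abstract, 12 months | covered | covered, no method given |
| Abstract, scans after stopping | covered | not addressed |
| Section 6.1.4 | covered | unclear |
| Section 6.1.5 | no text | no text |
| Table 6.1 and footnote f | covered | visits shown, no survival row |

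PFS and duration of response have several supports. OS after progression has one Abstract line and an uncertain reading of Section 6.1.4.

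**Step 2: how many patients could lose PFS or response follow-up?** Only those who stop without progression. Section 1.2.5 gives 3% to 24% discontinuation or withdrawal for adverse events at 2 mg: 27 x 0.03 = 0.8 and 27 x 0.24 = 6.5 patients. They are lost only if Section 3.5 overrides the scan rules above.

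**Step 3: illustration for OS if Section 3.5 is followed.** From the documents: 27 patients, 30 days (L = 0.986 months), a 12-month horizon. Assumed: median OS M of 5, 8 or 12 months, median time on drug mT of 2, 4 or 6 months, and a death hazard after stopping that is r = 1, 2 or 4 times the hazard h on treatment, with constant hazards.

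- Stop hazard: k = ln 2 / mT.
- With d = h + k - r h, true survival is S(t) = exp(-(h+k)t) + k[exp(-r h t) - exp(-(h+k)t)] / d. h is solved from S(M) = 0.5.
- Lost alive before month 12: 27 x k x exp(-r h L) x [1 - exp(-(h+k)(12 - L))] / (h + k).
- Among patients still followed, the ratio of recently stopped to still treated is q = k[exp(d x min(t, L)) - 1] / d. Kaplan-Meier sees the hazard h(1 + r q)/(1 + q), and its 12-month value is exp(-integral of that hazard).

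Worked case, M = 8, mT = 4, r = 2: k = 0.1733, h = 0.0607, d = 0.1126.

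- True 1-year OS: 0.0603 + 1.539 x (0.2330 - 0.0603) = 0.326, so 27 x 0.674 = 18.2 deaths.
- Lost alive: 27 x 0.1733 x 0.887 x 0.924 / 0.2340 = 16.4.
- Beyond the first month q = 0.181, so the hazard seen is 0.0607 x 1.361 / 1.181 = 0.0700. The cumulative hazard is about 0.835, and Kaplan-Meier gives exp(-0.835) = 0.434, a shift of +10.8 points.

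| r | Deaths in year 1, true and seen (M = 8, mT = 4) | Lost alive, M = 8, mT = 4 | Lost alive, all nine combinations | 1-year OS shift, all nine |
|---|---|---|---|---|
| 1 | 17.5 and 10.0 | 15.6 | 10.1 to 21.6 | 0 |
| 2 | 18.2 and 8.7 | 16.4 | 10.0 to 22.8 | +7.0 to +11.6 points |
| 4 | 18.7 and 7.5 | 17.0 | 9.5 to 23.5 | +11.3 to +20.5 points |

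**Step 4: precision.** At r = 1 and M = 8 the full-follow-up standard error is sqrt(0.354 x 0.646 / 27) = 0.092. Simulated trials of 27 patients under the 30-day rule (mT = 4) give about 0.18, so precision roughly halves even with no bias.

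**The case against.** The best defense is that Section 3.5 was meant as safety follow-up. Its second sentence concerns only adverse events, and the Abstract uses the same 30 days for safety. The planned timeline, with primary completion at 36 months and full completion at 48, also fits a further year of follow-up. This is plausible, and nothing shows an intention to stop OS at 30 days. But Section 3.5 carries the general title for follow-up and no safety limit, and even on this reading Section 6.1.5 stays empty.

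A reader might infer that survival after progression has no provision at all, because Section 6.1.4 names progression as an end point. The documents do not settle that. Section 6.1.4 and footnote f restrict scans to patients who have not progressed, a restriction that would be needless if progressed patients no longer attended, and Table 6.1 shows no stop at progression. The correct statement is that follow-up after progression is unclear. The visits described consist of examinations and laboratory tests, and no step records survival status for a patient who cannot attend.

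A reader might also infer that PFS and duration of response are damaged as badly as OS. They are not: three places in the protocol keep scans going after an early stop.

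Finally, the OS figures rest on inputs that the documents do not give, and the shift is zero at equal hazards. This stands, and no single shift should be quoted as the expected bias.

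**Conclusion.** The point holds as an inconsistency. Section 3.5 sets a 30-day limit that contradicts the Abstract, Section 6.1.4 and the 1-year OS endpoint, and the section that should describe survival follow-up is blank. The exposed endpoint is OS, which is secondary and descriptive. The ORR test, its alpha, its power and the sample size are essentially unaffected.

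If sites follow Section 3.5, and under the assumed medians, about 10 to 24 of 27 patients are lost alive before month 12. The 1-year OS shift is about 0 at equal hazards, about +7 to +12 points if the death hazard doubles after stopping, and about +11 to +21 points if it is four times as high. The loss of deaths needs no hazard difference; the bias does. The change should be made, because it is cheap and deaths not collected during the trial may be hard to recover later.

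**What to change.** 1. **Section 3.5:** limit the 30 days to safety follow-up. Add that every patient who stops trametinib, unless consent is withdrawn, continues tumor assessment until progression and survival follow-up to at least 12 months from first dose.
2. **Section 6.1.5 and Table 6.1:** describe survival contacts every 3 months by telephone or record review, including after progression, and add a survival row to the table.
3. **Section 6.1.4 and Abstract:** apply the progression stop to scans only, and use one follow-up duration in both places in place of 12 and 18 months.
4. **Table 5.14, pneumonitis row:** have the patient discontinue trametinib instead of the study, so that a drug stop does not count as removal under Section 3.5. Table 5.10 allows drug to continue or restart at Grades 1 to 3 where Table 5.14 does not. That conflict is a separate clinical decision.

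The cost is a few sentences, one short section, one new table row and one wording change. Survival contacts number at most about 27 x 4 = 108 in the first year, fewer as deaths occur, and many can be done from records. No scans are added beyond those already required.
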